Appendix A Schedule of Procedures Continued

	Screen							Υ	ear 1							Ye	ar 2			Y	ear3	
	1	W	W	W	W	W	W	W	W	W	W	W	W	W	W	W	W	W	W	W	W	W
Study Week	:S 4 weeks [⊥]	1	4	7	10	13	15	18	21	23	26	29	39	52	65	78	91	104	117	130	143	156
		D	D	D	D	D	D	D	D	D	D	D	D	D	D	D	D	D	D	D	D	D
Study Day	S-28 to S-1	1	22	43	64	85	99	120	141	155	176	197	267	358	449	540	631	722	813	904	995	1086
Visit Window(+/- Days)		0	7	7	7	7	7	7	7	7	7	7	7	7	10	10	10	10	10	10	10	10
Labs																						
Pregnancy Test ⁷ ·A	х3	X		X		X					X			X		X	XS	X	XS	X	XS	X
Chemistry PanelA(fasting)	хЗ	X	XS	X	XS	X	XS	XS	XS	XS	X	XS	XS	X	XS	X	XS	X	XS	X	XS	X
Additional Platele 1 ta 3 nd Serum Creatinine		x3 X XS X XS XS XS XS XS XS X X X X X X X X X X X X X																				
HematologI	хЗ	X	XS	X	XS	X	x8	XS	XS	XS	X	XS	XS	X	XS	X	XS	X	XS	X	XS	X
UrinalysisA	х3	X	XS	X	XS	X	x8	XS	XS	XS	X	XS	XS	X	XS	X	XS	X	XS	X	XS	X
24 hour Urine (serum creatinine required) ⁹	X																					
Thyroid PanelA	х3			X		X					X			X		X		X				X
PT, aPTT, INRA	х3			X		X					X			X		X		X				X
RetinolA(fasting)		X		X		X					X			X		X		X		X		X
hs-cRpA		X		X		X					X			X		X	XS	X	XS	X	XS	X
PD PanelA(fasting)		X		X		X		XS	XS		X		XS	X	XS	X	XS	X	XS	X	XS	X
NT-proBNPA		X		X		X		XS			X		XS	X	XS	X	XS	X	XS	X	XS	X
Immunogeniciif				X		X		XS			X		XS	X	XS	X	XS	X	XS	X	XS	X
PK TroughA		X		X		X		XS			X		XS	X	XS	X	XS	X	XS	X	XS	X

Appendix A Schedule of Procedures Continued

	Screen							Year	1							Ye	ar 2			Ye	ar3	
		W	W	W	W	W	W	W	W	W	W	W	W	W	W	W	W	W	W	W	W	W
Study Week	:S4 weeks ¹	1	4	7	10	13	15	18	21	23	26	29	39	52	65	78	91	104	117	130	143	156
		D	D	D	D	D	D	D	D	D	D	D	D	D	D	D	D	D	D	D	D	D
Study Day	S-28 to S-1	1	22	43	64	85	99	120	141	155	176	197	267	358	449	540	631	722	813	904	995	1086
Visit Window(+/- Days)		0	7	7	7	7	7	7	7	7	7	7	7	7	10	10	10	10	10	10	10	10
Efficacy Assessments																						
mNIS+7 Assessment ¹⁰											Χ			Χ		2X		Χ		Χ		2X
Norfolk QOL-DN ¹¹											Х			Χ		Х		Χ		Х		Χ
SF-36 Questionnaire											Χ			Χ		Χ		Χ		Χ		X
PND Score		х									Х			Χ		Х		Х		Х		Х
Body Weight (fasting)		Χ				Х					Х			Χ		Χ		X		Х		X
Transthoracic ECH0 ¹²		Χ												Χ		Χ		X				X

Appendix A Schedule of Procedures Continued

		Ve	ar4			Ye	ears		Early Term ¹⁴	Post- Treatment Evaluation
Study Week	Y4-W13	Y4-W26	Y4-W39	Y4-W52	Y5-W13	Y5-W26	Y5-W39	Y5-W52		Last Dose+ 13 weeks
Study Day										
Visit Window(+/- Days)	14	14	14	14	14	14	14	14	7	14
Informed Consent										
Inclusion/Exclusion										
ISIS 420915 Admin. (weekly)2	X	X	X	X	X	X	X	X		
Safety Assessments										
Full Physical Exam		X		X		X		X	X	X
Vital SignsA(BP ⁴ , HR, RR, temp)		X		X		X		X	X	X
ECGA(12-Lead, triplicate)		X		X		X		X	X	X
ERG Exams										
Ophthalmology Exams		X		X		X		X	X	
AE & Con Meds & Concomitant procedures	X	X	X	X	X	X	X	X	X	X
Phone Contact ⁶	X		X		X		X			

Appendix A Schedule of Procedures Continued

		Ye	ar4			Ye	ears		Early Term ¹⁴	Post- Treatment Evaluation
Study Week	Y4-W13	Y4-W26	Y4-W39	Y4-W52	Y5-W13	Y5-W26	Y5-W39	Y5-W52		Last Dose+ 13weeks
Study Day										
Visit Window (+/- Days)	14	14	14	14	14	14	14	14	7	14
Labs										
Pregnancy Test7A·		X	XB	X	XB	X	XB	X	X	X
Chemistry PanelA (fasting)	xa	X	x8	X	xa	X	xa	X	X	X
Additional Platelet and Serum Creatinine ¹³					See visit	schedule	Appendix	С		
Hematolog/	XB	X	XB	X	XB	X	XB	X	X	X
UrinalysisA	XB	X	XB	X	XB	X	XB	X	X	X
24 hour Urine (serum creatinine required) ⁹										
Thyroid PanelA		X		X				X	X	X
PT, aPTT, INRA		X		X				X	X	X
RetinolA(fasting)		X		X		X		X	X	X
hs-CRPA		X	XB	X	XB	X	XB	X	X	X
PD PanelA(fasting)	XB	X	XB	X	XB	X	XB	X	X	X
NT-proBNPA	XB	X	XB	X	XB	X	XB	X	X	X
Immunogenicit/				X				X	X	X
PK TroughA		X	XB	X		X	XB	X	X	X

Appendix A Schedule of Procedures Continued

		Ye	ar 4			Ye	ars		Early Term ¹⁴	Post- Treatment Evaluation
Study Week	Y4-W13	Y4-W26	Y4-W39	Y4-W52	Y5-W13	Y5-W26	Y5-W39	Y5-W52		Last Dose + 13 weeks
Study Day										
Visit Window (+/- Days)	14	14	14	14	14	14	14	14	7	14
Efficacy Assessments	;									
mNIS+7 Assessment ¹⁰									2X16	
NIS				Χ				Χ	x11	
Norfolk QOL-DN ¹¹				Х				Х	X	
SF-36 Questionnaire				Χ				X	X	
PND Score				Χ				Χ	X	
Body Weight (fasting)									X	x1s
Transthoracic ECH O									x1s	

Appendix A Schedule of Procedures Continued

Shaded columns represent non-clinic visits. Labs as indicated may be collected by the Sponsor's home healthcare service or by a local laboratory (with prior Sponsor approval). Patients also have the option to go to clinic for these visits.

Note: If not specifically labeled, "X" means anytime

- 1 For an individual patient, a maximum period of 4 weeks is allowed between a patient's last dose in ISIS 420915-CS2 (CS2 Week 65 visit) and initiation of dosing in this study (CS3 Day 1 visit). All screening assessments must be completed during this period. Longer periods may be considered after discussion and approval from the Study Medical Monitor
- 2 ISIS 420915 can be administered in the clinic or at home by the patient/caregiver. It is not necessary for ISIS 420915 to be administered on site during clinic visits. Clinic visits should occur on a dosing day, 7 days after the previous dose
- 3 Assessments from ISIS 420915-CS2 may be used for screening evaluation if they were obtained within 4 weeks of Study Day 1. A longer period may be considered after discussion and approval from the Study Medical Monitor
- 4 Blood pressure should be taken after the patient has been sitting for ≥ 5 min
- 5 A +/- 2-week window is given for ERG and ophthalmology examinations. The early termination ERG and ophthalmology examinations are only done if the patient discontinues treatment after ≥ 9 mo of dosing or unless deemed necessary by Investigator or Study Medical Monitor
- 6 To collect AEs, conmeds, and the general wellbeing of the patient
- 7 For females of childbearing potential only, by serum βhCG except on Day 1 by urine hCG (pre-dose)
- 8 To be collected by either a local laboratory (if approved by Sponsor), Sponsor appointed home healthcare service, or Study Center as arranged by the Study Center personnel
- 9 The 24-hour urine collection can be done any time during the screening period or during Week 1 on treatment. Serum creatinine blood draw required
- 10 If ISIS 420915 administration, ERG, or ophthalmology examinations are to be performed on the same day as a mNIS+7 assessment, they should be performed after the mNIS+7 assessment is complete. For the Week 78 and Week 156 visits, 2 mNIS+7 assessments will be performed on separate days. A maximum of 2 weeks from the visit (Week 78 or Week 156) will be allowed to complete both assessments
- 11 Norfolk QOL-DN should be the first assessment performed at the visit
- 12 Study Day 1 ECHO can be done any time in the screening period or up to 2 weeks after Day 1. The Day 1 ECHO is not done if the Week 65 ECHO was conducted in ISIS 420915-CS2. A +/- 2-week window is given for all other ECHOs
- 13 Weekly platelet and every 2-3 week serum creatinine monitoring is required throughout the treatment period and for a minimum of 6 weeks after the last dose of Study Drug (this includes early termination patients as well as patients that complete the full treatment period). The frequency of monitoring after 6 weeks from the last dose of Study Drug will be determined by the Study Medical Monitor. The visits required to collect platelets and serum creatinine not included in this table are shown in Appendix C. These visits may be completed in clinic, by home healthcare service, or by a local laboratory
- 14 Early termination should be performed at the time of withdrawal, ideally within 14 days from the last dose of Study Drug
- 15 Omit if following Year 4 or Year 5 treatment
- 16 Perform mNIS+7 only if early termination is from Year 1-3 treatment
- 17 Perform NIS only if early termination is from Year 4-5 treatment

Time (time is in reference to ISIS 420915 administration):

A Pre-dose

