6. STUDY PROCEDURES

6.1 Study Schedule

All required study procedures are outlined in Appendix A.

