To ensure maintenance of the study blind in the ongoing ISIS 420915-CS2 study, TTR, RBP4, retinol, and NT-proBNP from the first 13 weeks of treatment in this study will not be available to the Sponsor, Investigators, Study Center Personnel, or the patients until the ISIS 420915-CS2 study is unblinded.

The mNIS+7 assessment will be conducted at Weeks 26, 52, 78, 104, 130, and 156. The NIS assessment will be conducted at Y4-W52 and Y5-W52. The Norfolk QOL-DN questionnaire is conducted at Weeks 26, 52, 78, 104, 130, 156, and Y4-W52 and Y5-W52. The Norfolk QOL-DN questionnaire should be the first assessment performed at these visits. If ISIS 420915 administration, ERG, or ophthalmology examinations are to be performed on the same day as an mNIS+7 or NIS assessment, they should be performed after the mNIS+7 or NIS assessment is complete. For Week 78 and Week 156 visits, 2 mNIS+7 assessments will be performed on separate days. A maximum of 2 weeks from the visit (Week 78 or Week 156) will be allowed to complete both assessments.

For Weeks 4-52 there is a \pm 7-day visit window. After Week 52 the visit window is \pm 10-day. All reasonable attempts should be made to ensure compliance with the visit schedule as outlined in the schedule of procedures (Appendix A). However, if a visit does not occur or is delayed, all subsequent visits should be calculated based on the time elapsed since Day 1 rather than from the date of the previous visit.

The Study Day 1 ECHO can be done any time in the screening period or up to 2 weeks after Day 1. The Day 1 ECHO is not done if the Week 65 ECHO was conducted in ISIS 420915-CS2. A \pm 2-week window is given for all other ECHOs.

During the treatment period, an ophthalmology examination will be performed at Weeks 26, 52, 78, 104, 130, 156, and 2 times in each subsequent year (26^{th} and 52^{nd} week of each year). An ERG examination will be performed at Weeks 78 and 156. A window of \pm 2 weeks is allowed for these eye examinations. Early termination ERG and ophthalmology examinations are only done if the patient discontinues treatment after \geq 9 months of dosing or unless deemed necessary by Investigator or Study Medical Monitor.

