8.8 Discontinuation of Study Treatment

A patient must permanently discontinue study treatment for any of the following:

- The patient becomes pregnant. Report the pregnancy according to instructions in Section 9.5.4
- The patient withdraws consent
- The patient experiences an AE that necessitates permanent discontinuation of study treatment
- The patient develops laboratory test abnormalities that meet any of the stopping rules listed in Section 8.6

The reason for discontinuation of study treatment must be recorded in the eCRF and source documentation.

Patients who discontinue from treatment are encouraged to remain in the study. Every effort should be made to complete the ET visit and the post-treatment evaluation visits which include weekly platelet and every 2-3 week serum creatinine testing for 6 weeks after the last dose of Study Drug. If the patient declines to participate in the post-treatment evaluation visit, at a minimum the ET visit procedures should be performed at the time of withdrawal (See Appendix A) and ideally within 14 days from the last dose of ISIS 420915.

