Safety Endpoints: ERG and ophthalmology examinations	-Listings -On-treatment summary tables (CS3) -Post-treatment summary tables	-On-treatment (CS3 period): CS3 Study Day ls Date of assessment 5 Last dose date+ 28 days -Post-treatment: Date of assessment> last dose date+ 28 days -Visit defined by analysis visit window
Safety Endpoints: abnormal lab, worst ECG, meeting Stopping rule	-Listings -On-study summary tables (CS3)	-Abnormal lab analyses described in Sections 3.3.4.1 to 3.3.4.3 include post-baseline data collected from CS3 Study Day 1 up to the day of the patient's last contact date within the study
Safety Endpoints: AE	-Listings -On-treatment (CS3) summary tables -On-study (CS3) summary tables	-On-treatment: CS3 Study Day ls Date of assessment 5 Last dose date + 7 days -On-study summary tables includes all treatment emergent adverse event (TEAE) in the OLE study, including those with onset dates> last dose date + 7 days
Selected Safety Endpoints: abnormal lab and AEs	- Longitudinal safety summary for overall parent study and OLEstudy	- Longitudinal safety summary for overall parent study and OLE study include data collected from the first dose of ISIS 420915 in the parent study and ends on the day of the patient's last contact date within the study, (1) for subjects who enrolled in the OLE study, it is the last contact date within the OLE study; (2) for subjects who are not enrolled in the OLE study but had been administered ISIS 420915 in the parent study, it is the last contact date within the parent study.
Concomitant medications	-Listings -On-treatment (CS3) summary tables -On-study (CS3) summary table	-On-treatment: CS3 Study Day ls Date of assessment s Last dose date + 7 days -On-study summary tables includes all concomitant medication in the OLE study, including those with onset dates > last dose date+ 7 days
Immunogenicity	-Listings -On-study (CS2 and CS3)	-On-study summary/analysis tables include data collected from the CS2 Study Day 1 up to the day of the

Endpoint type	Output type	Comment/definition
	summary/ analysis tables	patient's last contact date within the study (showing both CS2 visits and CS3 visits) -Visit defined by analysis visit window.
PK	-Listings -On-study (CS3) summary/ analysis tables	-Summary/analysis tablesinclude data collected from CS3 Study Day 1 up to the day of the patient's last contact date within the study -PK concentration will be summarized based onnominal scheduled visits (showing CS3 visits)

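### The protocol text provides for a conditional early-termination ERG that the Appendix A grid does not mark, and on most stopping days the SAP has no window to bring such an ERG into the by-visit summary

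*Combined protocol and SAP*

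**What the plan says.** **Protocol.** Section 6.1.2 fixes the routine schedule: "An ERG examination will be performed at Weeks 78 and 156". It then adds: "Early termination ERG and ophthalmology examinations are only done if the patient discontinues treatment after" at least nine months of dosing, with a further route if the investigator or study medical monitor thinks the examination necessary. Footnote 5 of Appendix A repeats this rule: "The early termination ERG and ophthalmology examinations are only done if the patient discontinues treatment after" that same length of dosing, with the same further route. Section 6.1 states that "All required study procedures are outlined in Appendix A", and Sections 8.8 and 8.9 also send sites to Appendix A for the early-termination visit.

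On the grid page that carries the Early Term column, the "Ophthalmology Exams" row is marked at Early Term. The ERG row directly above it has no mark in any column. This is the only Early Term column in Appendix A, so it serves every treatment year. Footnote 16 confirms that: "Perform mNIS+7 only if early termination is from Year 1-3 treatment".

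**SAP.**
- Section 3.2.1.1.4 sets the on-treatment period for ERG at last dose plus 28 days, and for the other safety endpoints at last dose plus 7 days.
- Section 3.2.1.4 has a row headed "Safety Endpoints: ERG and ophthalmology examinations". It gives both examinations 28 days, plans listings plus on-treatment and post-treatment tables, and defines visits by analysis window.
- Appendix 3 Table 3 has two ERG windows: Week 78 (Days 510-570) and Week 156 (Days 1056-1116). Table 4, for follow-up, has no ERG or ophthalmology entry.
- Section 3.3.6 summarises ERG change from the ISIS 420915 baseline by parent-study group, lists all ERG results and tabulates patients who reach the ocular stopping rule. Section 9.1 does not remove the ERG summary from the final analysis.

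**The concern.** Safety is the primary objective, ERG is a listed safety endpoint (protocol Section 10.1.1), and ocular events related to vitamin A deficiency are an adverse event of special interest (SAP Section 3.3.2.1). For a patient who stops after nine months but before the Week 78 ERG, the early-termination ERG is the only routine ERG in this study.

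Two things stand between that ERG and the summary. First, whether it is done may depend on whether a site works from the grid marks or from the footnote, and on when the nine-month count is taken to start. Second, once done, it enters a by-visit table only if its date happens to fall in a Week 78 or Week 156 window. The ERG change-from-baseline summary would then describe mainly patients still on drug near those two visits.

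**Working it through.** The plan gives no figure to reproduce. The check compares the passages and then counts days.

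**1. Text against grid.** Section 6.1.2 and footnote 5 agree with each other. The grid agrees with them on ophthalmology and is silent on ERG.

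**2. Can the blank be explained?** Amendment 5 records that ERG is not performed in the added Years 4 and 5, which accounts for the blank Year 4-5 cells. It does not account for the Early Term cell, because that column also covers Years 1-3. Where an early-termination procedure depends on treatment year, Appendix A says so by footnote (15, 16 and 17). The ERG cell has neither a mark nor such a footnote. The blank also looks genuine as read: the neighbouring ophthalmology mark is present, and the ERG row on the Year 1-3 page keeps its Week 78 and Week 156 marks.

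**3. The nine-month count.** Protocol Section 2.4 gives patients randomised to active drug in CS2 65 weeks (15 months) of dosing before entry. SAP Section 1.1 plans 90 such patients and 45 on placebo. If CS2 dosing counts, a patient who completed active CS2 treatment meets the threshold on Day 1 of this study. If it does not, every patient reaches it at about Day 274. Neither text says which.

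**4. Window coverage.** Each ERG window is 570 − 510 + 1 = 61 days, or 1116 − 1056 + 1 = 61 days; together 122. Days in range = end − start + 1. Share outside = 1 − 122 / days in range. Nine months is an assumption: 9 × 30.4375 = Day 274, or 9 × 28 = Day 252.

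| First eligible day | To Day | Days in range | Inside a window | Outside |
|---|---|---|---|---|
| 274 | 1116 | 843 | 14.5% | 85.5% |
| 274 | 1814 | 1541 | 7.9% | 92.1% |
| 252 | 1116 | 865 | 14.1% | 85.9% |
| 252 | 1814 | 1563 | 7.8% | 92.2% |
| 1 (CS2 dosing counts, formerly active) | 1116 | 1116 | 10.9% | 89.1% |
| 1 (same) | 1814 | 1814 | 6.7% | 93.3% |

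Day 1116 is the end of the Week 156 window; Day 1814 is the Year 5 Week 52 target.

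**5. Post-treatment table.** Section 3.2.1.4 plans one for ERG with window-defined visits. Table 4 supplies no window, and the grid has no ERG mark in the Post-Treatment column.

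**6. Ophthalmology period.** It is 7 days by Section 3.2.1.1.4, where only ERG is excepted, and 28 days by Section 3.2.1.4. The visit-window text in Section 3.2.1.3 uses 7 days for safety assessments with no exception, even for ERG.

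**The case against.** The strongest reply is that this is a missing mark for a conditional procedure which two consistent texts describe. Several stronger readings are tempting and are not supported.

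- **That the grid forbids the ERG.** It does not; a blank cell is silent. Footnote 5 is itself part of Appendix A, so the pointers in Sections 6.1, 8.8 and 8.9 lead to the rule as well as to the grid.
- **That early-termination ERGs are lost to analysis.** Under SAP Section 3.2.1.3, assessments not used in by-visit tables are still listed and still count in determining treatment-emergent shifts or abnormalities. Section 3.3.6 lists every ERG. The gap is confined to the windowed tables.
- **That retinal or ocular safety follow-up fails at early termination.** Early-termination ophthalmology is consistent between text and grid. Symptom-triggered ERGs under protocol Section 8.5.3 and capture of ocular events of special interest do not depend on this cell.
- **That the ocular stopping rule is weakened.** Section 8.6.4 governs whether dosing stops. An ERG done because dosing has already stopped cannot trigger it.
- **That about nine in ten early-termination ERGs, or patients, would be missed.** The documents give no distribution of stopping dates. The percentages are shares of days, and the larger ones include Years 4 and 5, when no routine ERG is scheduled.

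The long interval before Week 78 without a scheduled ERG is likewise a feature of the design for every patient, not a result of the inconsistency.

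All of this narrows the point. It does not remove the mismatch between text and grid, the undefined nine-month count, or the missing windows.

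**Conclusion.** The concern holds in a limited form. The text provides for a conditional early-termination ERG that the grid does not mark, and the dosing that counts toward its threshold is undefined. Independently, the SAP's windows leave an ERG at early termination out of every by-visit table on about 85% of eligible days to Day 1116 and about 92% to Day 1814. Those figures take nine months as Day 274 and barely change at Day 252. If CS2 dosing counts, the shares for formerly active patients are 89% and 93%. The planned post-treatment ERG table has no window at all.

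The effect is limited to routine early-termination ERG data and to the change-from-baseline summary, which will describe mainly patients still on drug at Weeks 78 and 156. That merits correction because the endpoint serves the primary objective and the change is small. It does not put the safety evaluation as a whole in doubt. The ophthalmology discrepancy is real but has little effect, since Section 3.3.6 plans only listings of those findings.

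**What to change.** **Protocol.** Reconcile Section 6.1.2, footnote 5 and the Early Term cell of the ERG row so that sites have one instruction, and state whether CS2 dosing counts toward the nine months. This review does not choose the rule.

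**SAP.**
1. Add a last on-treatment ERG row to the change-from-baseline summary: each patient's last ERG up to 28 days after the last dose. It takes in any ERG obtained at early termination, however the protocol passages are reconciled. It pools different durations of dosing, so it should sit beside the Week 78 and Week 156 rows, not replace them.
2. Either add an ERG follow-up window to Appendix 3 Table 4 or drop the post-treatment ERG table from Section 3.2.1.4.
3. Use one on-treatment period for ophthalmology in Sections 3.2.1.1.4 and 3.2.1.4, carry it into Section 9.2.2.2 for the combined summaries, and add the ERG exception to the 7-day rule in Section 3.2.1.3.

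**Cost.** A minor protocol clarification, one extra summary row and a few lines of SAP text. SAP Section 1 already provides for stating changes from the planned analyses in the study report.

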Appendix B List of Laboratory Analytes

Appendix B List of Laboratory Analytes

Clinical Chemistry	Screening Tests	Hematology	Inflammatory
Panel	• FSH (women only)	Red blood cells	• Hs-CRP
• Sodium	• Serum βhCG	Hemoglobin	
• Potassium	Urine hCG	Hematocrit	Urinalysis ¹
• Chloride		• Platelets	• Color
Bicarbonate	Coagulation	White blood cells	Appearance
• Total protein	• aPTT (sec)	• WBC Differential (%	Specific gravity
• Albumin	• PT (sec)	and absolute)	• pH
• Calcium	• INR	 Neutrophils 	 P/C and Alb/C Ratios
• Magnesium		 Eosinophils 	• Protein
• Phosphorus	PD Panel ¹	 Basophils 	• Blood
• Glucose	Transthyretin	 Lymphocytes 	• Ketones
• BUN	 Retinol binding 	 Monocytes 	Urobilinogen
• Creatinine	protein 4 (RBP4)		Glucose
• Uric Acid		Thyroid Panel	Leukocyte esterase
Total bilirubin	24-hour Urine ⁴	• TSH	Nitrate
• Direct (conjugated)	• Creatinine	• Free T4 (FT4)	Microscopic
bilirubin	• Protein		examination ³
• Indirect	• Albumin	Pharmacokinetics ²	
(unconjugated) bilirubin		• ISIS 420915 levels in	
• ALT	Other	plasma	
• AST	• Retinol ¹		
Alkaline phosphatase	 Retinyl Palmitate 		
Arkanne phosphatase Creatine kinase	• NT-proBNP ¹		
Estimated creatinine	• Immunogenicity		
clearance (CKD-EPI)	(anti-ISIS 420915 antibodies)		
• Total IgG	announcs		
• Total IgM			
5			

- 1 Other biomarkers may be measured at the discretion of the Sponsor. Back-up samples will be collected and stored. For transthyretin and retinol, back-up samples may be analyzed in more sensitive transthyretin or retinol assays at the discretion of the Sponsor. Back-up urine samples may be analyzed for additional renal biomarkers
- 2 Plasma PK samples may also be used for profiling of drug binding proteins, bioanalytical method validation purposes, stability assessments, metabolite assessments, or to assess other actions of ISIS 420915 with plasma constituents
- Will be performed on abnormal findings (if the initial analysis is positive for protein, blood, nitrite, &/or leukocyte esterase) unless otherwise specified (to include: casts, crystals, bacteria, epithelial cells, RBC, WBC, yeast)
- 4 Serum creatinine blood draw required

